2 INTRODUCTION

2.1 BACKGROUND

Barrett's esophagus (BE) is a metaplastic change where the normal squamous epithelium of the esophagus is replaced by intestinal columnar epithelium, typically in response to chronic gastroesophageal reflux.^{1, 2} BE is a known risk factor for esophageal adenocarcinoma (EAC)³, a cancer with a high mortality rate and rapidly increasing incidence in developed countries.^{4, 5} The increased risk of cancer in BE patients leads to a need for surveillance, via endoscopy with random biopsies scattered across the affected tissue, using a biopsy pattern termed the "Seattle protocol".⁶ However, this pattern samples <5% of BE tissue, leading to substantial sampling error. In spite of evidence that endoscopic surveillance does not substantially impact cancer mortality,⁷ it is still the recommended management tool for in BE patients, due to a lack of proven alternatives.⁸

Because of this problem with sampling error, many optical techniques have been proposed for improving detection of pre-cancerous, dysplastic BE tissues but none have yet been widely adopted for routine use,⁸ due primarily to limited performance. While high resolution methods, such as confocal microscopy, have shown good sensitivity and specificity, the need to manually move a point probe to scan large areas of epithelium limits clinical utility. In comparison, wide area imaging approaches, such as autofluorescence imaging, view more tissue area but offer lower sensitivity and specificity. Recently, Thekke and Richards-Kortum advocated a multi-modality approach for optimal cervical screening.⁹ Similar approaches have been suggested for BE screening as well.¹⁰ The Investigators seek to create a novel imaging platform embodying this approach. This platform combines wide area imaging, using optical coherence tomography (OCT) to visualize esophageal epithelial regions, with high resolution, depth-resolved measurements of nuclear morphology, using angle-resolved LCI (a/LCI) to provide highly sensitive and specific detection of dysplasia.

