3 OBJECTIVES AND OUTCOMES

The purpose of this pilot study is to use the angle-resolved Low-Coherence Interferometry (a/LCI) and optical coherence tomography (OCT) technologies, developed by investigators on a small population of patients in an effort to gather information necessary for continuing development as a screening tool described above. Specifically, the study is designed to test the newly developed a/LCI-OCT device in human subjects to determine 1) whether adequate tissue contact can be attained to acquire high quality images, and 2) to identify if these images can discern whether the imaged tissue is squamous or BE epithelium.

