4 STUDY DESIGN

4.1 OVERALL DESIGN

This is a pilot study to test the operating characteristics of a newly developed optical coherence tomography (OCT) device in human subjects, and to collect data for further optimization of the OCT device.

Phase II of the study will consist of a combined probe consisting of angle-resolved Low-Coherence Interferometry (a/LCI) with developed optical coherence tomography (OCT).

Potential subjects will be presenting to a UNC Endoscopy unit for routine care endoscopy for clinical signs or symptoms. If eligible, informed consent will be obtained prior to undergoing routine care upper endoscopy. During the endoscopy, and prior to taking any routine care biopsies, the probe will be attached to the end of the endoscope and passed with the endoscope into the esophagus. The probe will make contact with the epithelium of the esophagus, and data will be collected as part of this research study to identify operating characteristics of the new device. Esophageal images and pictures will be obtained during the procedure and will be used in this study.

In Cohort A, if biopsies are taken for routine care, then results from those biopsies will be used in this study. Slides may be requested from clinical biopsies for use in this study, after they have yielded their results for routine care.

In Cohort B, co-localized research biopsies may be taken at the same location the probe is deployed. The indentation on the surface of the probe leaves a transient raised area of mucosa, which will aid in endoscopic identification of the site and allow for targeted concurrent biopsies.

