8.1.2.1 PROBE ADMINISTRATION, ESOPHAGEAL IMAGES, AND RESEARCH BIOPSIES

Subjects will proceed with routine care EGD, during which esophageal landmarks will be identified, and the OCT or a/LCI-OCT device administered. In brief, the probe will be affixed to the end of the endoscopy using a plastic band, in a manner similar to that used to deliver other devices into the esophagus. The device and endoscope tip will be passed through the posterior pharynx and the upper esophageal sphincter under direct endoscopic visualization. Areas of normal squamous epithelium can be easily identified endoscopically, as can areas of columnar mucosa in the esophagus, based on the endoscopic appearance. The OCT or a/LCI-OCT combined device will be apposed to both normal and columnar (Barrett's) tissue, by deflection of the endoscope tip. Images will be acquired by the device, as detailed below, and subjects enrolled in cohort B will also receive research-specific biopsies as detailed below. The indentation on the tip of the probe will create a transient tissue bump that is visible endoscopically to allow for concurrent research biopsies after images are taken. After acquisition of these images and research biopsies (as applicable), the remainder of the study will be performed as per the standard of care.

Erosions, erosive disease, and areas of inflammation will be avoided when placing the paddle for probe administration. Adequacy of device-to-epithelium contact will be measured based on the quality of the OCT image. In images with poor contact, esophageal mucosal layers are poorly defined. In this situation, the probe will be repositioned in an effort to improve image quality. A good image is that in which esophageal mucosal layers are clearly defined in the OCT image.

COHORT A:

During the procedure, the OCT device will be administered, and at least one white light image and at least one narrow band image will be taken from the following locations of the esophagus:

- 1) 3 centimeters above the top of the gastric folds (TGF-3)
- 2) 5 centimeters above the top of the gastric folds (TGF-5)
- 3) Any planned clinical biopsy locations

COHORT B:

During the procedure, the a/LCI-OCT device will be administered, and at least one white light image and at least one narrow band image will be taken from the following locations of the esophagus:

- 1) 3 centimeters above the top of the gastric folds (TGF-3)
- 2) 5 centimeters above the top of the gastric folds (TGF-5)

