9.4 STATISTICAL ANALYSES

This is a pilot study collecting data for OCT and a/LCI-OCT device optimization. This study will provide initial images for the investigational device, and depending on the device's accuracy in discerning tissue, these data will help form the basis for further investigations. Data analysis will consist of simple bivariate analysis, with endoscopy results being compared to a/LCI-OCT image results. Specifically, 2 x 2 tables of OCT, a/LCI-OCT, and endoscopy results will be constructed, with each imaging site being categorized as columnar versus squamous. Sensitivity will be defined as the proportion of sites correctly categorized by OCT, or a/LCI-OCT, using endoscopy results as the gold standard. Measures of variability of sensitivity results will be generated using non-parametric statistics.

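### Section 9.4 scores both probes only against endoscopic appearance, although the objective is squamous versus Barrett's tissue and histology is collected at imaged sites

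*Combined protocol and SAP*

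**What the plan says.** **Objective.** Section 3 and the synopsis give the second aim as "to identify if these images can discern whether the imaged tissue is squamous or BE epithelium". Section 2.1 describes Barrett's as a change in which "the normal squamous epithelium of the esophagus is replaced by intestinal columnar epithelium".

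**Analysis.** Section 9.4 states: "Data analysis will consist of simple bivariate analysis, with endoscopy results being compared to a/LCI-OCT image results". The 2 x 2 tables are built by site, "with each imaging site being categorized as columnar versus squamous". Sensitivity is then defined as the share of sites that either device classifies correctly, "using endoscopy results as the gold standard". Pathology is not named anywhere in section 9.4.

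**Histology in Cohort B.** The synopsis says that research biopsies at the probe location, in a subset of combined-probe participants, are taken so that imaging can be compared with biopsy, which it labels the gold standard. Section 2.3.1 gives the same purpose for the mucosal mark left by the dual-modality probe. Section 8.1.2.3 sends these biopsies for histopathology.

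**Histology in Cohort A.** The imaged locations in section 8.1.2.1 include "Any planned clinical biopsy locations". Section 4.1 adds that "if biopsies are taken for routine care, then results from those biopsies will be used in this study", and section 8.1.2.2 provides for obtaining reports and requesting slides. The synopsis and section 8.1.2.1 say how pathology is used: together with endoscopy and medical history, it assigns participants to groups.

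**The concern.** The objective concerns a tissue type, while the reference in 9.4 is a visual impression. Endoscopically columnar is a broader class than Barrett's as section 2.1 defines it, because columnar mucosa may lack the intestinal type. If 9.4 is followed as written, a columnar, non-intestinal site that the device calls columnar is a correct call. Against the study's own definition of Barrett's it would be a false positive.

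Two things are at stake. The second objective would be answered from appearance alone even where a tissue answer exists, including from biopsies taken for research. Also, the synopsis and 9.4 name different gold standards for the combined probe, so the reference could be chosen after the results are known. Section 9.2 sets a 70% sensitivity level for passing initial testing, and section 10.1.2 allows early termination on interim device accuracy. Both depend on which reference is meant.

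**Working it through.** **1. The plan's own figure.** Inputs from section 9.2: n = 14 per group, optimal sensitivity 0.95, lowest acceptable 0.70, power 85%. No alpha or decision rule is stated. Assume an exact one-sample binomial with one-sided alpha near 0.05, which gives a rule of at least 13 of 14:

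- Power = 14 x 0.95^13 x 0.05 + 0.95^14 = 0.3593 + 0.4877 = 0.847.
- Alpha = 14 x 0.70^13 x 0.30 + 0.70^14 = 0.0407 + 0.0068 = 0.0475.

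The 85% reproduces. The calculation has no term for error in the reference, so it cannot show what the choice of reference costs.

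**2. The texts side by side.**

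| Question | Cohort A | Cohort B |
|---|---|---|
| Histology at imaged sites? | Yes, if routine biopsies are taken (4.1, 8.1.2.1, 8.1.2.2) | Yes, research biopsies at the imaged site (8.1.2.3), though 1.3 and 4.1 make them optional |
| Site-to-biopsy match | Planned location only | Transient mucosal mark (2.3.1, 4.1) |
| Stated use of histology | Participant grouping (1.1, 8.1.2.1) | Comparison with imaging (1.1, 2.3.1) |
| Reference in 9.4 | Endoscopy | Endoscopy |

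Could the endoscopy results of 9.4 include biopsy? Section 8.1.2.1 lists endoscopy and clinical pathology as separate sources, so that is not the natural reading. Participant grouping does not fill the gap either, because 9.4 analyses sites.

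**3. Can the effect on sensitivity be sized?** Read sensitivity in its usual sense, as the share of endoscopically columnar sites that the device calls columnar. Let the true make-up of those sites be intestinal columnar (share I), non-intestinal columnar (share C) and squamous (share S), with I + C + S = 1. Let a, b and c be the chances that the device calls each type columnar. Then

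agreement with endoscopy = I x a + C x b + S x c.

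- If S = 0 and a = b = 0.95, agreement = 0.95 x (I + C) = 0.95 for any I. The endoscopic reference costs nothing in sensitivity.
- If b or c is below a, and the corresponding share is not zero, agreement falls below a.
- If the device repeats the endoscopic error, so that c is high, wrong calls are counted as right.

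The documents give none of I, C, S, b or c, so neither direction nor size follows. What does follow is that a fraction C x b of endoscopically columnar sites is counted as correct in 9.4 and would be a false positive for Barrett's. Only a pathology-referenced table can show it.

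**4. Precision of a histology-referenced estimate.** Exact 95% limits are the 0.025 quantile of Beta(x, n - x + 1) and the 0.975 quantile of Beta(x + 1, n - x). Assume one independent site per patient: 13/14 gives 66.1% to 99.8%, and 19/20 (the planned size of the Cohort B dysplasia group) gives 75.1% to 99.9%. Such tables are descriptive, in keeping with section 9.1.

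**The case against.** The strongest reply is that endoscopy is a deliberate and adequate working reference. Section 8.1.2.1 treats squamous and columnar mucosa as readily told apart by eye and uses columnar as its label for Barrett's. The synopsis lists no endpoints, and 9.4 describes a pilot for optimising the device. Cohort A pathology has a stated use in grouping, and nothing promises a site-level histology comparison there. Matching in Cohort A would also be crude: a 2-3 mm biopsy (2.3.3) against a paddle of about 23 x 14 mm (6.1.1), without the mark described for the dual-modality probe.

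Much of this stands. A reader might infer that the objective is not tested at all; it is tested, through a stated surrogate. A reader might also take the synopsis to make biopsy the gold standard throughout; that wording covers only a subset of combined-probe participants. The limits on Cohort A make its histology supportive and no more.

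The reply does not dispose of Cohort B. There the synopsis and 2.3.1 say why the biopsies are taken, and 9.4 leaves that comparison out. For Cohort A, the summary of changes gives evaluation of the device as the reason for adding the clinical pathology section, yet section 9.4 makes no use of it.

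**Conclusion.** The point holds as a gap and an inconsistency in the analysis plan for both cohorts. It is strongest for Cohort B, where the synopsis and 9.4 name different gold standards and must be reconciled. Followed as written, the plan gives no tissue-referenced accuracy for an objective defined by tissue type.

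No numerical effect on sensitivity can be claimed. A reader might infer that label error in endoscopy would sharply lower apparent sensitivity or the chance of passing. That requires the device to call many endoscopically columnar sites squamous. In a columnar-versus-squamous table, a non-intestinal columnar site correctly called columnar agrees with endoscopy, and nothing in the documents suggests that many sites judged columnar are really squamous. The 13-of-14 rule above is a reconstruction and not a rule of the plan, which in section 9.1 rules out hypothesis tests. A reader might also suppose that appearance is less reliable after eradication therapy; the documents say nothing on this.

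The conclusion rests on two readings: that the endoscopy results in 9.4 exclude pathology, and that Barrett's has the meaning given in 2.1.

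**What to change.** Keep the endoscopy-referenced 2 x 2 tables for all imaging sites, and add to section 9.4:

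> For imaged sites with a matched biopsy (Cohort B: co-localised research biopsies; Cohort A: clinical biopsies taken at the imaged location), a second set of 2 x 2 tables uses pathology as the reference. One table is columnar (with or without intestinal metaplasia) versus squamous; the other is intestinal metaplasia (BE) versus not. The number of imaged sites without matched histology is reported by group. Cohort B is the main histology-referenced analysis; Cohort A is supportive.

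The two tables give every columnar, non-intestinal result a defined place. State the rule for matching a biopsy to an imaged site before the data are read, and align the synopsis with 9.4 on the reference standard for the combined probe.

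The cost is a few extra tables. No patients or procedures are added, because the protocol already provides for collecting the data. The limits should be reported with the tables. Biopsied sites are a selected subset that mainly informs sensitivity, especially in Cohort A, where asymptomatic controls without a biopsy are taken to be squamous. Cohort A matching is by location only, without the tissue mark.

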10 SUPPORTING DOCUMENTATION AND OPERATIONAL CONSIDERATIONS

10.1 REGULATORY, ETHICAL, AND STUDY OVERSIGHT CONSIDERATIONS

10.1.1 INFORMED CONSENT PROCESS

10.1.1.1 CONSENT AND OTHER INFORMATIONAL DOCUMENTS PROVIDED TO PARTICIPANTS

Consent forms describing in detail the study intervention, study procedures, and risks are given to the participant and written documentation of informed consent is required prior to starting intervention/administering study intervention.

10.1.1.2 CONSENT PROCEDURES AND DOCUMENTATION

In obtaining and documenting informed consent, the investigator must comply with applicable regulatory requirements (e.g., 45 CFR Part 46, 21 CFR Part 50, 21 CFR Part 56) and should adhere to ICH GCP.

Informed consent is a process that is initiated prior to the individual's agreeing to participate in the study and continues throughout the individual's study participation. Consent forms will be Institutional Review Board (IRB)-approved and the participant will be asked to read and review the document. The investigator or designee will explain the research study to the participant and answer any questions that may arise. A verbal explanation will be provided in terms suited to the participant's comprehension of the purposes, procedures, and potential risks of the study and of their rights as research participants. Participants will have the opportunity to carefully review the written consent form and ask questions prior to signing. The participants should have the opportunity to discuss the study with their family or surrogates or think about it prior to agreeing to participate. The participant will sign the informed consent document prior to any procedures being done specifically for the study. Participants must be informed that participation is voluntary and that they may withdraw from the study at any time, without prejudice. A copy of the informed consent document will be given to the participants for their records. The informed consent process will be conducted and documented in the source document (including the date), and the form signed, before the participant undergoes any study-specific procedures. The rights and welfare of the participants will be protected by emphasizing to them that the quality of their medical care will not be adversely affected if they decline to participate in this study.

10.1.2 STUDY DISCONTINUATION AND CLOSURE

This study may be temporarily suspended or prematurely terminated if there is sufficient reasonable cause. Written notification, documenting the reason for study suspension or termination, will be provided by the suspending or terminating party to investigators, funding agency, the Investigational Device Exemption (IDE) sponsor and regulatory authorities. If the study is prematurely terminated or suspended, the Principal Investigator (PI) will promptly inform study participants, the Institutional Review Board (IRB), and sponsor and will provide the reason(s) for the termination or suspension.

Circumstances that may warrant termination or suspension include, but are not limited to:

- Determination of unexpected, significant, or unacceptable risk to participants
- Demonstration of efficacy that would warrant stopping
- Insufficient compliance to protocol requirements
- Data that are not sufficiently complete and/or evaluable
- Determination that the primary endpoint has been met
- Determination of futility

Study may resume once concerns about safety, protocol compliance, and data quality are addressed, and satisfy the sponsor, IRB and/or Food and Drug Administration (FDA).

This is a pilot study with very low risk, therefore it is not anticipated the study will be terminated or suspended. However, the data safety monitor (DSM) will monitor the trial for unanticipated adverse events on regular (3 month) intervals, as well as performing interim assessments of the performance characteristics of the imaging devices, which may merit consideration of premature termination of the study should the device prove inadequately accurate for clinical use, or conversely be so highly accurate that further enrollment would not be likely to change the results of the trial.

10.1.3 CONFIDENTIALITY AND PRIVACY

Participant confidentiality and privacy is strictly held in trust by the participating investigators, their staff, and the sponsor(s) and their interventions. This confidentiality is extended to cover testing of biological samples and genetic tests in addition to the clinical information relating to participants. Therefore, the study protocol, documentation, data, and all other information generated will be held in strict confidence. No information concerning the study or the data will be released to any unauthorized third party without prior written approval of the sponsor.

All research activities will be conducted in as private a setting as possible.

The study monitor, other authorized representatives of the sponsor, representatives of the Institutional Review Board (IRB), regulatory agencies or company supplying study product may inspect all documents and records required to be maintained by the investigator, including but not limited to, medical records (office, clinic, or hospital) and pharmacy records for the participants in this study. The clinical study site will permit access to such records.

The study participant's contact information will be securely stored at each clinical site for internal use during the study. At the end of the study, all records will continue to be kept in a secure location for as long a period as dictated by the reviewing IRB, Institutional policies, or sponsor requirements.

Study participant research data, which is for purposes of statistical analysis and scientific reporting, will be transmitted to and stored at the University of North Carolina at Chapel Hill and Duke University. This will not include the participant's contact or identifying information other than date of birth and procedure dates (limited data set). Rather, individual participants and their research data will be identified by a unique study identification number. The study data entry and study management systems used by the University of North Carolina at Chapel Hill and Duke University will be secured and password protected. At the end of the study, all study databases will be coded and archived at the University of North Carolina at Chapel Hill and Duke University. One master list linking subjects to their code will be maintained securely by the PI, and separate from the research data.

10.1.4 FUTURE USE OF DATA

Data collected for this study will be analyzed and stored at the University of North Carolina at Chapel Hill and Duke University. After the study is completed, the coded, archived data will be stored at the University of North Carolina at Chapel Hill and Duke University, for use by other researchers including those outside of the study.

When the study is completed, access to study data and/or samples will be provided through investigators at the University of North Carolina at Chapel Hill and Duke University.

